The aim is to test the feasibility of a brief online CBT-intervention at the Swedish national gambling helpline's counselling service, more specifically: pilot-test of a short online CBT-program in connection to an initial counselling session at the gambling helpline.

Method and materials

Design

A pragmatic randomized controlled pilot trial examining feasibility of an additional brief online CBT-program in connection to an initial counselling session in the helpline. The study participants will, after an initial counselling session with the helpline, be randomized to either a brief online CBT-program or to log their gambling habits for six weeks.

Outcomes

The main outcome is feasibility of conducting the study, secondary outcomes are net losses to gambling, days gambling, problem gambling severity level, gambling urges, self-efficacy in gambling situations, psychosocial health and general social functioning.

Participants

Study participants will be recruited from the helpline's counselling service and webpage. Gamblers' scoring above 3 points on the PGSI scale are eligible for inclusion. Other inclusion criteria are:

- Aged over 18 years
- Good enough skills in the Swedish language
- Access to the Internet

Exclusion criteria are:

- Being involved in a treatment research study the previous 3 months

- Receiving other treatment for PG
- Being on a non-stable drug treatment for any psychiatric disorder
- Showing signs of severe depression

Randomization

Participants will be randomized using block randomization with varying block sizes (ranging between 2 to 8 participants per block) to ensure balanced groups.

Data collection

Data will be collected at baseline, weekly during the treatment, after the treatment, and 6 weeks after the end of treatment.

Intervention

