Feasibility will be analysed using mainly descriptive statistics. To analyse the longitudinal data a three-level regression model will be used. The highest level in the hierarchy consists of the therapist, the second level is the client and at the lowest level are the repeated measurements made on the clients. The main outcome in the longitudinal part of the study will be net losses, and based on earlier knowledge it is known that this outcome have a distribution that is far from a normal distribution. It has a distribution with high peaks at both ends of the measured values. Therefore, the regression models used to analyse the longitudinal data will not be linear models but rather zero-inflated or alternatively hurdle models based on either a Poisson distribution or a negative binomial distribution.

Ethical considerations

Since the patient group is fairly new and society's help is limited, there is a risk that patients with too extensive need of support apply to participate in the intervention study. To make sure that no one is left without help, participants who for any reason are excluded from the study will be referred to help in their vicinity. The helpline has a record of addiction and psychiatric care to all of Sweden's municipalities and county councils.

Further, participants will be systematically followed up within the study, which enables the research group to have a constant supervision of the treatment process. Participants who are still experiencing problems after intervention termination will be referred to help in their vicinity.

Participants who end the intervention without telling, will be contacted via telephone up to 3 times to check further participation, and will, if necessary, be offered a referral to further treatment. Deviations will be reported in the participant's paper journal. Personal data will be handled according to the Swedish Data Protection Act.

In previous outcome studies participants have benefitted from the treatment they have received. It is likely to believe that those who participate in the study will benefit from the intervention. It is also likely to believe that future problem gamblers will benefit from the study.

References

1. Statens Folkhälsoinstitut. Spel om pengar och spelproblem i Sverige 2009 / 2010. Statens folkhälsoinstitut; 2010.

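### As worded, the SAP requires zero-inflated or hurdle count models for all longitudinal data, although the only reason given is the distribution of net losses; the score-type secondary outcomes need a model of their own

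*Combined protocol and SAP*

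**What the plan says.** The Statistical analyses plan (SAP) section opens its longitudinal part with "To analyse the longitudinal data a three-level regression model will be used"; the levels are therapist, client and repeated measurement. It then gives the reason for the type of model. That reason begins "The main outcome in the longitudinal part of the study will be net losses, and based on earlier knowledge it is known that this outcome" and goes on to say that the outcome is far from normal. The shape is described as follows: "It has a distribution with high peaks at both ends of the measured values". The conclusion is "Therefore, the regression models used to analyse the longitudinal data will not be linear models but rather zero-inflated or alternatively hurdle models". As the base, Poisson and negative binomial are both allowed. No rule is given for choosing between the two distributions, or between zero-inflated and hurdle forms.

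The Outcomes section makes feasibility the main outcome and adds: "secondary outcomes are net losses to gambling, days gambling, problem gambling severity level, gambling urges, self-efficacy in gambling situations, psychosocial health and general social functioning". No model other than the one above is named for any of these. The Participants section gives the entry rule, "scoring above 3 points on the PGSI scale are eligible for inclusion". This is the only place where the PGSI appears. The documents name no instrument or score range for the five score-type outcomes, and no window for days gambling.

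**The concern.** The argument runs from one outcome to all of them. A spike at zero in net losses is a reason to consider a zero part for net losses. It says nothing about scores for severity, urges, self-efficacy, health or functioning. Yet linear models are ruled out for the longitudinal data as a whole.

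Applied to a score, the prescribed family can go wrong in three ways.

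- **The zero part may have nothing to estimate.** If severity is measured with the PGSI, the entry rule removes zeros at baseline, and a score centred well above zero has few at any visit.
- **The effect measures do not suit a score.** The output would be a ratio of mean scores and odds of belonging to the zero group. The ratio depends on where the scale happens to start, and the odds have no clear meaning for a rating.
- **Poisson fixes the variance at the mean.** A score has no reason to obey this. If its variance is larger, intervals are too narrow; if smaller, too wide. Negative binomial adds variance but cannot remove it, and neither distribution has an upper bound.

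At stake are the secondary effect estimates and intervals, which may inform a later trial.

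**Working it through.** **No figure to reproduce.** The documents give no sample size, significance level, mean or SD. The 5% level, 30 clients per arm, and all means, SDs and score ranges below are assumptions.

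**Step 1: scope.** The three-level sentence and the no-linear-models sentence are both about the longitudinal data, without exception. Net losses is called the main outcome of that part, so it is not the only one. The Outcomes section lists seven secondary outcomes: 7 − 1 (net losses) = 6 others, of which one is days gambling and 6 − 1 = 5 are score-type.

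**Step 2: Poisson error for a score, client effects conditioned out.** Take one pre and one post score per client, n clients per arm, mean μ and within-client SD σ. The group-by-time estimate is the difference between arms in log(post total / pre total). With few or no zeros, the positive part of a hurdle Poisson model is practically an ordinary Poisson model.

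- Model SE = √(4/(nμ))
- True SE ≈ √(4σ²/(nμ²))
- Ratio = √μ/σ, so n cancels
- Rejection under the null = 2Φ(−1.96 × ratio)

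| Assumed scale | μ | σ | Model SE (n = 30) | True SE | Ratio | Rejection |
|---|---|---|---|---|---|---|
| 0–100 | 60 | 12 | 0.047 | 0.073 | 0.65 | 21% |
| 0–100 | 60 | 15 | 0.047 | 0.091 | 0.52 | 31% |
| 0–27 | 14 | 3 | 0.098 | 0.078 | 1.25 | 1.5% |
| 0–27 | 14 | 2 | 0.098 | 0.052 | 1.87 | 0.02% |

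Simulating the same test, with scores rounded and cut at the ends of the scale, gave about 20–29% for the 0–100 scale and 0–1% for the 0–27 scale. Repeat runs ranged from 18% to 30% and from 0% to about 1.5%. The ratio is exactly 1 only when σ² = μ.

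**Step 3: negative binomial.** This was a null simulation with one time point, 50 per arm, up to 400 data sets and no zero part. The ratio is model SE to true SE.

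| Assumed scale | Poisson ratio (rejection) | Negative binomial ratio (rejection) |
|---|---|---|
| 0–100, mean 60, SD 20 | 0.39 (46.5%) | 1.07 (3.5%) |
| 0–27, mean 14, SD 5 | 0.79 (12%) | 1.08 (4.2%) |
| 0–27, mean 14, SD 3 | 1.34 (0.2%) | 1.31 (0%); 251 of 400 fits usable |

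Negative binomial repairs the over-dispersed cases and fails in the under-dispersed one. None of these scenarios produced enough zeros for a hurdle part to be fitted.

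**Step 4: days gambling, assumed 0–7.** For zero-inflated or hurdle Poisson, the SE ratio of the count part lay between 0.87 and 1.23 over four assumed shapes, with rejection of 1% to 9.5%. The standard errors are therefore only modestly off. The misfit is at the ceiling. For a U-shaped week with about 21% at 0 and 21% at 7, the fitted hurdle Poisson (λ = 4.37) predicts about 6% at exactly 7 days and puts about 6% above 7, which cannot occur.

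**The case against.** **The rule may be meant for net losses alone.** It follows directly from two sentences about that outcome. This reading is possible. It would leave six of the seven secondary outcomes with no model, so text is needed either way.

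**Negative binomial is allowed.** This stands. A reader might infer that following the SAP makes the intervals for six secondary outcomes wrong. The documents do not support that: the choice of distribution is open, and step 3 shows negative binomial near nominal for over-dispersed scores. What remains is that Poisson is equally allowed, no selection rule is given, and under-dispersion is not repaired.

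**Single-time-point figures are not the planned analysis.** This also stands. A reader might take the 46.5% in step 3, or the roughly 50% found for a 0–100 scale with mean 60 and SD 25, as the error rate of this trial. Those runs have no client level. With a Poisson client random intercept (assumed 30 per arm, three time points, intraclass correlation 0.5–0.7, 300 null data sets), the average group effect rejected 4–7%. Group-by-time, however, still rejected 25–41% on the 0–100 scale and 0–2% on the two narrower scales. Client effects therefore shrink the problem without removing it.

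**Days gambling is a count, often with many zeros.** This is correct. A reader might infer that its standard errors are wrong too; step 4 does not bear that out.

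**Instruments are unknown, and zeros can appear at follow-up.** Both are true. That severity is scored by PGSI is an inference from the entry rule, and the rule excludes zeros only at baseline.

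**The stakes are limited.** Feasibility is the main outcome and is analysed mainly descriptively. That limits the weight of the point.

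**Conclusion.** The point holds for the five score-type outcomes. As worded, the SAP excludes linear models and prescribes a count family whose only justification concerns a different outcome. The zero part may be inestimable, the effects would be hard to interpret and, if Poisson is chosen, intervals may err in either direction. Under the assumed scales, the group-by-time test at nominal 5% rejects about 20–29% (0–100, within-client SD 12–15) or 0–1% (0–27, within-client SD 2–3). These figures illustrate the mechanism. They rest on assumed means, SDs and ranges, use two time points and leave out the therapist level. They do not estimate this trial's error rate. For days gambling the only issue is the ignored upper bound. This should be changed, but it does not threaten the main, descriptive feasibility outcome.

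**What to change.** Change two sentences in the SAP section.

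1. Limit the zero-inflated/hurdle sentence to the outcomes it is justified for: net losses and, if wished, days gambling. For days gambling, a binomial or beta-binomial mixed model with the days in the period as denominator would respect the ceiling. Where a count model stays, add how Poisson or negative binomial will be chosen.
2. State that severity, urges, self-efficacy, psychosocial health and social functioning will be analysed with a linear mixed model in the same therapist–client–measurement hierarchy, with robust or bootstrap standard errors.

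The cost is those two sentences and slightly more programming; data collection does not change. The fix does not settle whether a zero part is enough for net losses, which the SAP describes as peaking at both ends.

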The internet-based CBT program that is the intervention in the study is developed by the research group and is based on CBT treatment for problematic gambling (see 18). The program have elements of psycho-education, functional analysis on gambling situations, behavioural activation, reflections on thoughts about gambling and relapse prevention, and basically the same motivational increasing principals that is used in the Motivation Interviewing (MI) method. The program consists of four modules that are given during six weeks (week 1, 2, 4, and 6 after randomization). Each module has its own team with text to read and exercises. When a module is completed, the participants receive feedback from a counsellor via a messaging system in the web platform. The feedback aims to highlight and strengthen the client's self-determination and own ability to change their behaviour. In the last module, the progress made and tips for further support are summarized. Themes for the four treatment modules are as follows:

Week 1: Objective of treatment, psycho-education, functional analysis on gambling

Week 2: Functional analysis on gambling situations, thoughts on gambling and behavioral activation

Week 4: Behavioural activation and functional analysis on gambling-free activities

Week 6: Relapse plane: to maintain a gambling-free life with focus on handling risk situations and engage in gambling-free activities.

The ordinary counsellors at the helpline will be the counsellors in the study and will be educated in the CBT method before the study starts. They all have a long experience to work with persons who are problematic gamblers and they will receive continuous supervision by a certified psychologist. The written feedback given to the counsellors will be reviewed to ensure that the treatment is given according to the CBT method.

Statistical analyses plan (SAP)

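### Does the protocol's only re-contact rule leave missed assessments, and controls who stop logging, without any follow-up?

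*Combined protocol and SAP*

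**What the plan says.** The re-contact rule stands under Ethical considerations: "Participants who end the intervention without telling, will be contacted via telephone up to 3 times to check further participation". The same sentence goes on to offer a referral where one is needed. Just before it, the section says that "participants will be systematically followed up within the study", tied to supervision of the treatment process. It then says that people whose problems persist once the intervention is over will be referred to local help.

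The Design section states that participants will "be randomized to either a brief online CBT-program or to log their gambling habits for six weeks". The Intervention section reserves the key word for one arm: "The internet-based CBT program that is the intervention in the study is developed by the research group". The Data collection section gives the schedule for the whole sample: "Data will be collected at baseline, weekly during the treatment, after the treatment, and 6 weeks after the end of treatment". It adds no reminder or re-contact step. The Outcomes section says "The main outcome is feasibility of conducting the study", and the SAP analyses feasibility mainly descriptively. Net losses is the main outcome of the longitudinal part.

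**The concern.** Two gaps appear when these sections are read together.

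- **Trigger.** A person who completes the four modules, or the six weeks of logging, and then misses the last follow-up has not ended the intervention without telling. The rule does not reach that person in either arm, and nothing else in the document does.
- **Arms.** If the intervention means the CBT program, controls who stop logging would not be called while CBT participants who drop out would be.

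Retention is a natural measure of feasibility, although the protocol does not name it as one. A descriptive retention figure depends on how hard people are pursued. If that effort differed by arm, retention and the completeness of net-loss data could differ for reasons unrelated to the treatment. The SAP states no handling of missing data.

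**Working it through.** The plan gives no figure to reproduce. The check is mainly a comparison of texts, followed by a test of whether any size can be attached.

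**1. Is it the only rule?** Yes. No other section mentions reminders, re-contact, missed assessments or retention targets. The statement about systematic follow-up names no trigger, contact mode or number of attempts.

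**2. Whom does the trigger miss?**

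- *During the six weeks.* Ending without telling has no operational definition. Missed weekly entries are the likely way to notice it. For controls, logging is the assigned activity and may overlap with the weekly measurement.
- *End of treatment.* The last module is given in week 6, so a missed end-of-treatment assessment may itself be the sign of a silent exit. The rule may or may not apply.
- *Six weeks after the end.* A participant who finished and then misses this assessment is clearly outside the rule. This is the only occasion for which the gap is certain.

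**3. Does the rule cover one arm or both?** For one arm: the Intervention section equates the word with the CBT program. For both:

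- The rule says participants, with no arm named.
- Checking further participation can mean participation in the study.
- The sentence directly before it, on people with persisting problems, also names no arm.
- The same section uses the word broadly elsewhere: "there is a risk that patients with too extensive need of support apply to participate in the intervention study", and the expectation that "those who participate in the study will benefit from the intervention".
- The Data collection section speaks of the treatment period for the whole sample.

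The one-sided reading is possible but not established.

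**4. Can it be sized?** If only one arm is called, the retention gap is

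gap = share stopping × (share of stoppers recovered with calls − share recovered without).

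The documents supply none of these inputs; every value below is assumed.

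| Share stopping | Recovered with / without calls | Gap (percentage points) |
|---|---|---|
| any | equal (both arms called, or calls recover no data) | 0 |
| 20% | 50% / 25% | 0.2 × 0.25 = 5 |
| 40% | 50% / 25% | 0.4 × 0.25 = 10 |
| 50% | 50% / 10% | 0.5 × 0.40 = 20 |

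For finishers who miss the last follow-up, share = finishing × missing. With 50–80% finishing and 10–30% of them missing, this runs from 0.5 × 0.10 = 5% to 0.8 × 0.30 = 24% of those randomised, again entirely by assumption. Nothing in the documents gives the size or direction of a bias in net losses.

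**5. Would an added call rule remove the problem?** Suppose up to three calls were added for each of the two later assessments, in both arms, with the existing rule left alone. The maximum is 3 × 2 = 6 extra calls per participant. On the one-sided reading, a CBT participant who stops could then receive 3 + 6 = 9 calls against 6 for a control. The imbalance would remain.

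**The case for a change.** The best case for a change is that contact effort is part of what a feasibility trial measures. Retention cannot be read, or carried into the planning of a larger trial, unless one knows how it was obtained and whether both arms were treated alike. Writing the procedure down would be cheap: if 20–50% missed each assessment (assumed), at most 6 × 0.2 = 1.2 to 6 × 0.5 = 3.0 additional calls per participant randomised. The general promise of systematic follow-up does not fill the gap, and the welfare purpose of the quoted rule only confirms that no retention procedure was written.

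Much of this stands. The text is silent on missed assessments, and the key word is used in two senses. What does not stand is the step from silence to a faulty result. The quoted rule is judged against a task it does not claim: it checks participation and offers referral. Nothing in the plan forbids chasing a missed follow-up or says that controls are to be left alone. Whether the calls recover outcome data at all is unknown, so even a one-sided rule need not alter retention of data.

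**Conclusion.** No change to the plan is called for. What the text shows is a missing operational detail, the handling of a missed assessment, and one word used both narrowly and broadly. The gap is certain only for participants who finish and then miss the assessment six weeks after treatment. For controls it depends on a reading that the adjacent sentences do not favour.

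Study staff would ordinarily pursue missed follow-ups whether or not the protocol says so, and feasibility is to be described rather than tested. No stated rule has been shown to produce a wrong result. The size is undetermined: the illustrative retention gap starts at 0 and reaches 20 points only by assuming that half of the participants stop, that only one arm is called, and that calls raise recovery from 10% to 50%.

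The conclusion assumes that staff follow up both arms alike in practice. Evidence that controls were deliberately not contacted would reopen the point.
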